IV. Project Design and Procedures.

- a. Performance Measurement.** The primary outcome is UTI within 14 +/- 2 days post-surgery. A UTI is defined as an infection in any part of your urinary system which may include the kidneys, ureters, bladder, and urethra. Most infections involve the lower urinary tract (bladder and urethra), and are treatable with antibiotics. If a UTI spreads to the kidney, it can become a more serious complication. Women are at a greater risk of developing a UTI than men are. Pre-operative antibiotics will be collected to determine if this directly affects the outcome of a UTI. Visits to the ED for urinary pain, incontinence, or fever will also be followed for determination of UTI. Participants will provide a urine sample 0-24 hours before surgery. The sample will be tested with a rapid urine analysis (UA) test. This measure was chosen so that study UAs results are not to be confused with standard UAs conducted with samples collected after catheter placement. Participants will be followed up by research staff ~24 hours post-surgery for a second UA test. A third UA will be conducted at the patients' post-op check. At follow-up visits, participants will also

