be assessed for symptoms of UTI since surgery by assessment of: urethral discomfort, suprapubic tenderness or pelvic pain, sense of urinary urgency, frequency or dysuria, fever, antibiotic use, and clinical and laboratory data suggesting infection (UA with +leukocyte esterase +/- nitrates, urine culture with $>10^5$ bacterial colony forming units per mL (CFU)). Asymptomatic bacteriuria will be considered a UTI for this study (defined as $>10^5$ CFU/mL on urine culture). Patients who are treated with antibiotics for UTI without laboratory data suggesting infection will be included in UTI group. For participants reporting ED visits prior to 14 +/- 2 day visit, ED reports will be obtained and an assessment will be made regarding the symptomatic UTI diagnosis. Those meeting these criteria will be followed with symptom and laboratory analysis. All positive UA test will be confirmed by laboratory analysis for final diagnosis. Results of +leukocyte esterase +/- nitrites will be considered abnormal. If a diagnosis of UTI does not exist in the patient chart outside of study, the patient's clinical picture will be evaluated independently by 2 separate care providers to determine if meeting criteria for UTI (symptomatic bacteriuria as defined above). If there is discrepancy a third provider will be the determining opinion. Participants meeting the primary endpoint (UTI) will be discontinued from the study following.

Secondary outcomes include: hospital length of stay, readmissions, antibiotic use at the time of surgery and post-surgery. Measures of UTI, and secondary outcomes will be collected from observation during study visits and from the patient medical charts., If closed drainage system was disrupted during placement (to back fill bladder intra-operatively), and method of catheter discontinuation ("fill and pull" versus "pull and void" methods) will be collected for comparison between the groups for analysis as a possible confounding variables.

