Additional secondary outcomes to be evaluated will include patient discomfort with catheter, tolerability of catheter, length of hospital stay, and number of post-operative evaluations required. A cost-analysis will be performed as a secondary endpoint based on this cost factors (length of hospital stay, readmission, additional clinic/ED visits, antibiotic costs). Costs of hospital days, clinic visits, other appointments, and antibiotics will be standardized for evaluation based on literature for cost analysis in gynecologic oncology literature.

b. Target population. Women undergoing extended surgery lasting >1 hour and requiring urinary catheter will be eligible for enrollment. All patients will have surgery performed by one of the trained Gynecologic Oncologists at the University of Colorado Hospital.

Inclusion criteria will include:

- 1) women 18-89 years of age
- 2) admitted for surgery lasting >1 hour and requiring urinary catheter,
- 3) have normal urine analysis within 24 hours pre-surgery, and
- 4) able to provide informed consent.

Women with dialysis, chronic urinary infection, and current infection will not be eligible to participate. Women who are pregnant or breast feeding will not be included in the study. Men will not be included because of their lower incidence of UTIs compared to our female population.

The null hypothesis is that there will be no difference in UTI rates between the standard of care catheter placement and the sterile protocol placement. If we use the current rates of UTI after catheter placement described above at 40%, we would need to enroll 100 patients per arm (total 200) to see a 50% reduction in UTI rates in the intervention group with an alpha of 0.05 and a power of 0.84. The Gynecologic Oncology services averages around 5 surgical patients who would be eligible for this study per week. We anticipate needing between 10-12 months to complete enrollment.

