The Principal Investigator will be responsible for the conduct of this study, overseeing participant safety, executing the data and safety monitoring (DSM) plan, and complying with all reporting requirements to local and federal authorities. This oversight will be accomplished through additional oversight from the Data and Safety Monitoring Committee (DSMC) at the University of Colorado Cancer Center (CU Cancer Center). The DSMC is responsible for ensuring data quality and study participant safety for all trials at the CU Cancer Center. A summary of the DSMC's activities is as follows:

- Conduct of internal audits
- Ongoing review of all serious adverse events (SAEs), unanticipated problems (UAPs) and reportable adverse events (AEs)
- Has the authority to close and/or suspend studies for safety or conduct issues
- May submit recommendations for corrective actions to the CU Cancer Center's Executive Committee

Per the CU Cancer Center Institutional DSM Plan, SAEs, UAPs and reportable AEs are reported to the DSMC, IRB and the sponsor (if applicable) per study protocol. All SAEs, UAPs and

reportable AEs are to be reported to the DSMC within 5 business days of the Principal Investigator receiving notification of the occurrence.

Study audits conducted by the DSMC will consist of a review of the regulatory documents, consent forms, and source data verification.

Documentation of the audit conducted by the DSMC will then need to be submitted to the IRB of record at the time of the IRB's continuing review of this trial.

Potential scientific problems:

This study proposes the use of a simplified peri-operative catheter insertion protocol aimed at reducing the rates of urinary tract infections after catheter placement. If effective this could be represent a low-cost, low-effort intervention however obtaining a clinically meaningful response may be the biggest limitation of this study. Although UTI rates are relatively high after post-surgical catheter placement and there have been several studies showing some reductions, there are numerous additional studies which have failed to show a difference. Our goal here is not to merely achieve a statistically significant but rather a clinically meaningful response. We therefore powered our study to look for at least a 50% reduction in the rate of UTI's.

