Additionally, there is and will remain practice variations in catheter placement. While we hope to find a difference despite these differences, it is possible that the intervention may give a false impression of improvement simply by focusing attention on a protocol. While it is difficult to remove confounding from any study, randomization and analysis adjustments will be used to reduce as much as possible.

VI. Data Analysis Plan:

This study will assess a population of patients undergoing extended surgery requiring catheter placement to be performed by the Gynecologic Oncology service. De-identified patient data will be collected into OnCore and exported to SPSS for data analysis. Initial summary statistics will be performed to report the distribution of the data, including variable means, medians, proportions and missing data.

An intent-to-treat analysis will be conducted. All participants receiving treatment per protocol will be included in the final analysis. If there are any participants who are randomized but do not receive the intended treatment, we will document the reasons for their being withheld treatment.

For the primary outcome measure of UTI rate at each of the time points (24 hours and 14 +/- 2 days), we will perform a test of binomial proportions for testing the null hypothesis of no difference between the treatment arms. Because we are performing tests at two time points, we will adjust for the multiple comparisons using Bonferroni's method.

We will also explore the association between treatment arms and other covariates (symptomatic and demographics factors) using bivariate methods. The particular analysis method for testing the association between them will depend on the distribution of the covariates. For example, symptomatic presentation variables (fever, pelvic pain, sense of urgency or dysuria, and antibiotic use) are categorical, and their association with treatment arm will be evaluated with a chi-square statistic.

For demographic variables, Student's *t*-test (for continuous variables) and chi-square tests (for categorical variables) will be used to compare the two treatment arms. Variables found to be significant in these bivariate analyses will be included in multivariable analysis using logistic regression. Logistic regression models will be used to identify significant independent predictors associated with UTI

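### The stated power of 0.84 ignores the Bonferroni split over two time points; at 0.025 per test the 14-day comparison has about 0.76 to 0.81

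*Combined protocol and SAP*

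**What the plan says.** Section IV.a names one primary outcome: "The primary outcome is UTI within 14 +/- 2 days post-surgery". Section IV.b takes a 40% UTI rate under standard care and asks for 100 patients per arm to see a "50% reduction in UTI rates in the intervention group with an alpha of 0.05 and a power of 0.84". It mentions no division of alpha, and it names neither the test nor its sidedness. Section V, under potential scientific problems, relies on that calculation: "We therefore powered our study to look for at least a 50% reduction in the rate of" UTI.

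Section VI describes a different primary analysis. Its key sentence opens "For the primary outcome measure of UTI rate at each of the time points (24 hours and 14 +/- 2 days" and continues "we will perform a test of binomial proportions for testing the null hypothesis of no difference between the treatment arms". It then adds "Because we are performing tests at two time points, we will adjust for the multiple comparisons using" Bonferroni's method. No overall alpha is given there. Later in section VI, directly after the description of the logistic models, a significance threshold of 0.005 appears without a stated scope.

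**The concern.** The sample size section assumes one test at 0.05, while the analysis section commits to two tests of the primary outcome with alpha divided between them. The same 100 patients per arm cannot give the same power at a stricter level, and the document never recalculates.

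Two things are at stake. The first is the claim in section V that the trial is powered for a halving of the UTI rate. The second is that the threshold deciding success is left open. Sections IV.a and IV.b support 14 days alone at 0.05, section VI supports two time points at a reduced level, and 0.005 appears as well. A choice among these made after the data are seen could change the conclusion.

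**Working it through.** **Inputs.** From IV.b: control rate 0.40; 50% reduction, so 0.20 on intervention; n = 100 per arm; alpha 0.05; power 0.84. From IV.c: 1:1 allocation. From VI: two tests with Bonferroni. Assumed: two-sided testing, an overall alpha of 0.05 (so 0.05/2 = 0.025 per test), the 40% and 20% rates applying to the 14-day endpoint, and all 100 per arm evaluable.

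**Formula.** Two proportions, pooled variance under the null:

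Power = Φ[(d − c − z × SE0) / SE1]

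- d = 0.40 − 0.20 = 0.20
- c = 0 without continuity correction, or 1/n = 0.01 with it
- SE0 = √(2 × 0.30 × 0.70 / 100) = 0.0648
- SE1 = √((0.40 × 0.60 + 0.20 × 0.80) / 100) = 0.0632
- z = 1.960 at two-sided 0.05, and 2.241 at two-sided 0.025

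**Step 1: reproduce the plan's figure at 0.05.**

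- Corrected: (0.19 − 0.1270) / 0.0632 = 0.996, power 0.840
- Uncorrected: (0.20 − 0.1270) / 0.0632 = 1.154, power 0.876
- Fisher's exact test, by full enumeration: 0.844
- One-sided 0.05: 0.930 uncorrected, 0.906 corrected

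The corrected sample-size formula also returns exactly 100 per arm for power 0.84. So the printed pair of 100 and 0.84 fits one two-sided test, corrected or exact, at an undivided 0.05. Both features are inferred, because the document states neither.

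**Step 2: apply the split.**

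- Corrected: (0.19 − 0.1453) / 0.0632 = 0.707, power 0.760
- Uncorrected: (0.20 − 0.1453) / 0.0632 = 0.866, power 0.807
- Fisher: 0.769

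| Two-sided alpha | Uncorrected | Corrected | Fisher |
|---|---|---|---|
| 0.05 | 0.876 | 0.840 | 0.844 |
| 0.025 | 0.807 | 0.760 | 0.769 |

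**Step 3: allow for success at either time point.** Bonferroni lets either test succeed, so the 14-day power is a floor for the rule as a whole. The documents give no 24-hour rate. Assume the same 50% reduction at 24 hours, with 10% to 90% of the 14-day UTIs already present by then. In 400,000 simulated trials per setting, power for at least one success is 0.77 to 0.79 (corrected or Fisher) and 0.82 to 0.83 (uncorrected). It can pass 0.84 if the early effect is larger: assumed 24-hour rates of 20% and 6% give 0.864 (corrected) and 0.905 (uncorrected).

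**Step 4: where the levels disagree.** With 40/100 control events, 0.05 and 0.025 differ at one intervention count only. That count is 26 for the uncorrected test (p = 0.035), or 25 for the corrected test (p = 0.035) and Fisher (p = 0.034).

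**Step 5: size that restores 0.84 at 0.025.** 109 per arm uncorrected (power 0.8425) or 119 corrected (0.8433).

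**Side check on 0.005.** Only if that threshold governed the primary test would power fall to 0.55 (corrected) to 0.61 (uncorrected). Its position suggests that it belongs to the logistic models or is a slip for 0.05.

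**The case against.** The best case for the plan is that the loss is small and partly rests on an inferred test. Section VI asks only for a test of binomial proportions. Read as uncorrected, the 14-day power at 0.025 is 0.81, and an unpooled-variance formula gives 0.82. A success at 24 hours would also count, which under equal effects lifts the uncorrected figure to 0.82 to 0.83. Type I error is protected. The 40% input is itself loose: section II says near 40%, and the risk section gives it as an upper figure. With a control rate of 35% (an assumption) and the same 50% reduction, power at an undivided 0.05 would already be 0.76 to 0.81.

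Much of this stands as a limit on size. The 0.76 end applies if the test behind the 0.84 is also the analysis test, and the uncertainty in the control rate matters about as much as the split. It does not remove the mismatch. Within any one method the split costs about 6 to 8 points. The formulas that give 0.81 or 0.82 at 0.025 give 0.876 or 0.885 at 0.05, so they are not the source of the 0.84. The gain from a 24-hour success cannot be claimed without a 24-hour rate.

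It is also fair that the primary outcome in IV.a already reads as cumulative, so stating that early UTIs count is a clarification and not a new element.

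**Conclusion.** The concern holds. The power in IV.b does not reflect the multiplicity rule in VI. For the 14-day test at 0.025, power is 0.76 to 0.81, which is 3 to 8 points below the printed 0.84; like for like with the method that reproduces 0.84, it falls from 0.84 to 0.76. The chance of missing a true halving of the rate is 19% to 24%, against 16%.

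This rests on an overall alpha of 0.05, two-sided testing, the 40% and 20% rates at 14 days, and no loss of evaluable patients. The plan makes no dropout allowance, and any loss would lower power further. The shortfall is moderate; it should be fixed, but it does not threaten the trial. The unexplained 0.005 is a secondary point and adds no weight to this judgement.

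**What to change.** Make a dated amendment to IV.b and VI before outcome data by arm are seen. The documents do not show how far accrual has gone.

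**Preferred.** Name one primary test in VI, for example: *The proportion of participants with a UTI at any time from surgery through day 14 +/- 2, including any found at 24 hours, will be compared between arms by a two-sided continuity-corrected chi-square (or Fisher's exact) test at alpha 0.05.* Make the 24-hour comparison secondary and drop the Bonferroni split. Counting 24-hour events should be explicit because section IV.a says "Participants meeting the primary endpoint (UTI) will be discontinued from the study following", so a day-14 analysis limited to those attending that visit would lose them. The stated 0.84 then holds with 100 evaluable per arm. An uncorrected test is also acceptable if IV.b is restated to match (0.876). Cost: no extra patients, but the 24-hour result can no longer deliver primary success.

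**Alternative.** Keep both time points at 0.025 each, say that success on either suffices, and restate the 14-day power in IV.b as about 0.76 (0.81 if uncorrected). Cost: no extra patients, but a less favourable stated power.

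Enlarging the trial is not needed for consistency. If 0.84 had to be kept at 0.025, it would take 109 to 119 per arm, or 18 to 38 more patients in total. Section IV.b says "We anticipate needing between 10-12 months to complete enrollment", which for 200 patients is 16.7 to 20 a month, so the extra time would be 18/20 = 0.9 to 38/16.7 = 2.3 months.

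Under either option, name the test and its sidedness in IV.b, and either correct the 0.005 to the intended level or limit it in words to the logistic models. If it is kept for the models, explain why adjusted and primary comparisons of the same endpoint use different thresholds.

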c. Study Design and Research Method. We will conduct a single-site Randomized Control Trial (RCT) in order to examine the use of an aseptic protocol for catheter insertion during gynecologic oncology surgeries for quality improvement. This study will take place at the UCH inpatient surgical unit of gynecologic oncology. The catheter protocol for QI will be conducted in the operating room prior to surgery and will not increase prep time or operating room time. Follow-up will be conducted during standard outpatient care visits and will also not increase clinic use time.

The intervention in this study is a controlled aseptic pre-treatment protocol for catheter use in the operating room involving dipping the tip of the catheter into betadine prior to insertion and maintaining catheter in the sterile plastic sleeve during preparation, insertion and post-operatively to avoid excess exposure to the environment. The Physician performing the operation will be responsible for inserting the catheter. Patients with normal UA pre-surgery will be randomized 1:1 to one of two arms prior to surgery:

- 1) Aseptic protocol for catheter insertion using betadine treated catheter and maintaining plastic sleeve on catheter *or*
- 2) SOC catheter insertion in which catheter is inserted right out of package/non-treated catheter.

Prior to study initiation, the PI will train providers on the proper use of the protocol. Catheter insertion procedures will be documented in the operation note following surgery. Compliance will be measured by adherence to both betadine use and maintenance of plastic sleeve. Standard of care practices for infection control are to be conducted by providers on all participants. This includes: hand hygiene, inserting catheters for appropriate indications, remove catheters when no longer needed, maintain a close system keeping bag and tubing below the bladder.

We will collect general patient demographics to assure similarities between the randomized groups. These will include age, race/ethnicity, BMI, insurance type, diagnosis (reason for surgery), history of diabetes, menopausal status, and smoking status. MRN data will be collected in order to pull data directly into the OnCore data management system.

d. Study Procedures

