occurrence for each treatment arm. We will fit separate logistic regression models for UTI occurrence at the two time points. The logistic model will allow for control of study covariates simultaneously. A p-value of <0.005 will be used to demonstrate statistical significance. IBM SPSS version 23 will be used for all statistical analyses.

Secondary outcomes will include a cost-analysis of the two treatment protocols and a patient satisfaction query in regards to the catheter procedure.

- Cost-analysis: The cost-effectiveness of the interventions will be assessed using hospital stay, readmissions, clinic/ED visits, and antibiotic costs per patient during the study period. An estimate of patient care costs will be derived using standard cost data described in the literature. The two groups will be compared in terms of average cost of treatment with a 95% confidence interval using a Bayesian statistic.
- Satisfaction: Patient satisfaction with the catheter protocol will be measured using a Likert-like scale questionnaire. Responses between the two groups will be compared using a Mann-Whitney-Wilcoxon statistic.

VII. Summarized Knowledge to be gained:

This study aims to reduce the incidence of urinary tract infections in patients undergoing surgery on the Gynecologic Oncology service through an aseptic protocol for placement. Such quality improvement studies are needed to help reduce complication rates and health-care costs.

VIII. References:

1. Septimus, E.J. and J. Moody, *Prevention of Device-Related Healthcare-Associated Infections*. F1000Res, 2016. **5**.
2. Stephan, F., et al., *Reduction of urinary tract infection and antibiotic use after surgery: a controlled, prospective, before-after intervention study*. Clin Infect Dis, 2006. **42**(11): p. 1544-51.
3. Barbadoro, P., et al., *Catheter-associated urinary tract infection: Role of the setting of catheter insertion*. Am J Infect Control, 2015. **43**(7): p. 707-10.
4. Amine, A.E., M.O. Helal, and W.M. Bakr, *Evaluation of an intervention program to prevent hospital-acquired catheter-associated urinary tract infections in an ICU in a rural Egypt hospital*. GMS Hyg Infect Control, 2014. **9**(2): p. Doc15.
5. Singh, S., et al., *Surveillance of device-associated infections at a teaching hospital in rural Gujarat--India*. Indian J Med Microbiol, 2010. **28**(4): p. 342-7.

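### No baseline covariate is named for the cost comparison and length of stay has no stated analysis, so prognostic data already collected are not used to sharpen either one

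*Combined protocol and SAP*

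**What the plan says.** **Baseline data.** Section IV.c gives the purpose: "We will collect general patient demographics to assure similarities between the randomized groups". The list follows: "These will include age, race/ethnicity, BMI, insurance type, diagnosis (reason for surgery), history of diabetes, menopausal status, and smoking status". Section IV.d places clinical diagnosis and health history at Visit 1, ahead of randomization at Visit 2.

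**Cost.** Section IV.a: "A cost-analysis will be performed as a secondary endpoint based on this cost factors (length of hospital stay, readmission, additional clinic/ED visits, antibiotic costs". Unit costs are to be standardized from the literature. The method is in Section VI: "The two groups will be compared in terms of average cost of treatment with a 95% confidence interval using a Bayesian statistic". No covariate, model or prior is named.

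**Length of stay.** Section IV.a names it as a secondary outcome and counts it among the cost components. Section VI gives it no test, model or summary contrast of its own.

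**Adjustment.** Section VI carries variables that differ significantly in the bivariate comparisons into logistic regression for UTI, with a separate model at each of the two time points. This is the only multivariable model in the plan. Under potential scientific problems, Section V says in general terms that randomization and adjustment in the analysis will be used to limit confounding. It names neither outcome nor covariates.

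**The concern.** Eligibility covers women aged 18 to 89 having any gynecologic oncology operation of more than one hour that needs a catheter, so the case mix may be wide. With standardized unit costs, differences in cost between women come from resource use: days, readmissions, visits and antibiotics. If reason for surgery, age, BMI or diabetes predict those quantities, an analysis that leaves them out keeps explainable variance in the arm difference and gives a wider interval than the data require.

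Section I makes hospital stay, readmission and cost-effectiveness part of the rationale, so the precision of these comparisons matters. The plan's only stated rule for choosing covariates selects those that happen to differ between arms. If that rule were borrowed for cost, it would select on chance imbalance and not on prognostic value, and the choice would be made after seeing the data.

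**Working it through.** **Inputs.** From Sections IV.b and IV.c: 100 women per arm, 1:1 allocation, no stratification stated, UTI 40% against 20%, alpha 0.05 (sidedness not stated; two-sided assumed), power 0.84. The documents give no SD for cost or stay and no R². Results are therefore in SD units over an assumed range of R².

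**1. The plan's own figure.** The plan states "we would need to enroll 100 patients per arm (total 200" patients "to see a 50% reduction in UTI rates in the intervention group with an alpha of 0.05 and a power of 0.84". For two proportions:

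- Uncorrected: n₀ = [1.960·sqrt(2·0.3·0.7) + 0.994·sqrt(0.24 + 0.16)]² / 0.20² = 90.2, so 91 per arm.
- Continuity-corrected: n = (n₀/4)·[1 + sqrt(1 + 4/(n₀·0.20))]² = 99.9, so 100 per arm.

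The figure reproduces. It concerns UTI only. The plan states no power or precision for cost or stay.

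**2. Where the baseline variables are used.**

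| Outcome | Stated analysis | Baseline covariates |
|---|---|---|
| Baseline similarity | t-tests, chi-square | they are the variables tested |
| UTI, two time points | test of proportions; logistic regression | in the logistic models, if different between arms |
| Cost | average cost with 95% interval | none named |
| Length of stay | none | none |

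**3. Effect of adjustment at 100 per arm.** The unadjusted 95% half-width is 1.960·sqrt(2/100) = 0.277 SD. The difference detectable with 80% power is (1.960 + 0.842)·sqrt(2/100) = 0.396 SD. Adjustment multiplies both by f = sqrt(1 − R²). The equivalent unadjusted sample is 100/(1 − R²) per arm. Power at 0.396 SD is Φ(2.802/f − 1.960).

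| Assumed R² | f | Half-width (SD) | Detectable difference (SD) | Equivalent n per arm | Power at 0.396 SD |
|---|---|---|---|---|---|
| 0 | 1.000 | 0.277 | 0.396 | 100 | 0.80 |
| 0.05 | 0.975 | 0.270 | 0.386 | 105 | 0.82 |
| 0.10 | 0.949 | 0.263 | 0.376 | 111 | 0.84 |
| 0.20 | 0.894 | 0.248 | 0.354 | 125 | 0.88 |
| 0.30 | 0.837 | 0.232 | 0.331 | 143 | 0.92 |
| 0.50 | 0.707 | 0.196 | 0.280 | 200 | 0.98 |

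**4. The same in days, as illustration.** Assume three equal-sized diagnosis groups; the mean stays and within-group coefficients of variation (CV) are also assumed. The SE of the arm difference is sqrt(variance·2/100), using total variance without adjustment and within-group variance with it.

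- Means 2, 3, 4 days, CV 0.7: between-group variance 0.667, within 0.49·(4 + 9 + 16)/3 = 4.737. The SE falls from 0.33 to 0.31.
- Means 1.5, 3, 5.5 days, CV 0.5: between 2.722, within 0.25·(2.25 + 9 + 30.25)/3 = 3.458. The SE falls from 0.35 to 0.26.

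**5. Price of adjusting.** Three diagnosis groups (two indicators) plus age, BMI and diabetes make five covariate terms. Estimating them inflates the variance by about (200 − 3)/(200 − 5 − 3) = 197/192 = 1.026, or 1.3% in width. The figures in step 3 ignore this. Adjustment breaks even at R² = 5/197 = 0.025.

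**The case against.** **The unadjusted comparison is valid.** Under 1:1 randomization it is unbiased, and its standard error already allows for chance imbalance. This stands. A reader might infer that the cost result would be biased by case mix, but nothing in the documents supports that.

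**Silence is not a specification of an unadjusted analysis.** Section VI speaks only of a Bayesian statistic, and Section V promises adjustment. This stands in part. The promise is general, and the only adjusted model in the plan is a logistic one for UTI, which cannot serve cost or days.

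**The size rests on assumption.** This stands. The documents give no R², SD or mean stay. The variable collected is the reason for surgery, not the procedure or surgical approach, so it may explain less than hoped.

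**No conclusion is likely to change.** If there were 3 fewer extended stays per 100 women, each adding 5 days (both assumed), the mean difference would be 0.15 days. Taking favourable standard errors of 0.34 days unadjusted and 0.25 adjusted, power would rise only from about 7% to about 9%. This stands as a limit on the benefit.

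**Regression does not repair incomplete follow-up.** Section IV.a discontinues women who reach the UTI endpoint, while Section IV.d collects stay, readmission and antibiotic data at Visit 4. Chart review may fill the gap. This is a separate matter.

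**Three further inferences are tempting but unsupported.**

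- That the baseline variables serve only to check similarity: Section VI also carries those that differ between arms into the UTI models.
- That length of stay is to be compared as raw averages: the plan states no comparison for it at all.
- That the plan itself implies 6 against 3 extended stays or readmissions per 100 (0.40·0.15 and 0.20·0.15): the 15% in Section II refers to post-operative complications in general, and the 40% includes asymptomatic cases (Section IV.e).

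**Conclusion.** The point holds as one of precision on secondary outcomes. No covariate is named for cost, no analysis is stated for length of stay, and the prognostic variables already collected enter neither.

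The gain from adjustment is small if they explain little and becomes material at an R² of about 0.30, where it is worth 43 extra women per arm. The documents cannot say which applies. The primary comparison, its sample size and its error rate are untouched. Adjustment is worth making because it uses data already in hand and costs almost nothing in precision even if the covariates turn out to be weak.

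**What to change.** In Section VI, replace the cost sentence with a regression of total cost per woman on arm plus a fixed list: diagnosis category, age, BMI and history of diabetes. Enter all of them whether or not they differ between arms. Report the adjusted difference in mean cost with a 95% interval suited to skewed costs (robust or bootstrap), or specify the equivalent Bayesian model with its priors. State that length of stay is analysed the same way. Report the unadjusted differences as a sensitivity analysis.

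The change takes a few sentences and needs no new patients or measurements. The one extra task is to define the diagnosis categories, from the pre-operative reason for surgery, before the data are analysed.
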